1.7. Evaluation of Best Overall Response

The best overall response is the best response recorded from the start of the treatment until the end of treatment. The patient's best response assignment will depend on the findings of both target and non-target disease and will also take into consideration the appearance of new lesions.

Revised Response Evaluation Criteria in Solid Tumors (RECIST) Version 1.1 ([Eisenhauer, 2009](#)) is summarized in the table below.

Response According to Revised Response Evaluation Criteria in Solid Tumors (Version 1.1) in Patients with Target (and Non-Target) Lesions

Target Lesions	Non-target Lesions	New Lesions	Overall Response*
CR	CR	No	CR
CR	Non-CR/non-PD	No	PR
CR	Not evaluated	No	PR
PR	Non-CR/non-PD/not all evaluated	No	PR
SD	Non-CR/non-PD/not all evaluated	No	SD
Not all evaluated	Non-PD	No	NE
PD	Any	Yes or no	PD
Any	PD*	Yes or no	PD
Any	Any	Yes	PD

Abbreviations: CR=complete response; PD=progressive disease; PR=partial response; SD=stable disease; NE=inevaluable.

*In exceptional circumstances, unequivocal progression in non-target lesions may be accepted as PD.

Note: Patients with a global deterioration of health status requiring discontinuation of treatment without objective evidence of disease progression at that time should be reported as “*symptomatic deterioration.*” Every effort should be made to document the objective progression even after discontinuation of treatment.

APPENDIX 5. DIGITAL PHOTOGRAPHIC PROCEDURES

In this study, radiology studies will be the primary method of tumor assessment. For patients with externally visible lesions, the investigator may wish to supplement response assessments with digital medical photography. This Appendix provides guidelines for optional digital medical photography.

Image Capture

- Close-up view with millimeter scale of the target area of the CSCC
- Global view of the target CSCC area

Equipment

- Camera: Canon SL1 with Ranging Lights
- Lens: 60 mm Canon Lens
- Flash: Canfield TwinFlash RL
- Millimeter scale attachment
- Dedicated laptop with Canfield Capture Application (software includes capturing, viewing and transferring images)
- Canfield Tracing and Analysis application
- Standardized background material

The supplied equipment is to be used exclusively for this study. No modification, adjustments, or repairs of the camera equipment are to be undertaken without the expressed instruction of Canfield Scientific, Inc.

Canfield will provide each study site with the necessary hardware as well as technical support as needed. All supplied photographic equipment remains the property of the Sponsor.

Proper Patient Preparation and Positioning:

In these clinical photographs for the duration of the study, the only variable allowed to change is the skin condition itself. Therefore, anything extraneous to the condition (furniture, etc) is to be eliminated from the photographic field, starting at the entry visit through the final visit. The necessity of good end-of-study photographs should be stressed to patients to ensure their cooperation. Lighting, framing, exposure, and reproduction ratios must be held constant. In the end, the images should read like a time-lapse movie.

In the close-up view, the area of interest is the individual target lesion itself. In the global view, the area of interest includes the target lesion as well as relevant anatomical landmarks, eg, side of face, side of neck, upper torso, full view of shoulder, etc. Photographs should be taken with the camera positioned at the same vertical height as the center of area of interest. Further, all shots should be made with the axis of the camera lens perpendicular to the surface of area of interest when possible. Glancing shots where the camera lens is not perpendicular to the patient's area of interest are to be avoided as these photographic angles may distort the image perspective yielding inaccuracies when measurement of lesions is performed on photos by central review.

The supplied standardized background material is to be used. Do not use wrinkled or crimped material.

The Canfield Capture software controls the setting of the camera specific to the protocol. The lens is set for auto focusing. The **close-up view** is accomplished using the attached standardized mm scale. The **global view** is accomplished when the ranging lights converge on the target area. Any doubt as to the correctness of the photographic technique should result in an immediate re-shoot. At the baseline visit, a **profile view** (perpendicular to the skin's plane) will also be obtained of each lesion to capture any projection above the skin. For all lesions in which the baseline profile view demonstrates significant projection above the skin, defined as ≥ 15 mm, the profile view will also be obtained at subsequent scheduled clinical assessments of response.

For each global view and each close-up view, an unannotated photograph must be taken followed by a manually annotated photograph.

For response assessments, Canfield imaging software should be used to assure that the photograph is taken at the same position and angle as the Baseline photograph. The annotated image from the prior visit should be referenced on the laptop screen prior to making annotations on the new image.

Photographic Procedures:

1. Prior to capturing the patient images using the camera system, the photographer launches the Canfield Scientific Canfield Capture Application by selecting the icon from the desktop.
2. The photographer either creates a New Patient for an initial visit or, for a return subject, highlights the appropriate existing Patient ID listed in the Canfield Capture database. The visit name (as per study schedule) is selected by the photographer and the image date is captured by the software.
3. With the patient's target area positioned correctly in front of the camera system, the Photographer adjusts the camera distance for accurate system focus. The first capture is a Close-up view of patient's target CSCC area(s) using the attached mm scale, consisting of one individual CSCC lesion. The second capture is Global view of patient's target CSCC area(s), consisting of up to two individual CSCC lesions. For the global view the camera is moved closer to or further away from the target until the two green ranging lights converge to become one dot.
4. The Photographer captures the image and is then prompted to review image acceptability. The Photographer either accepts the image and moves on to the next capture or does not accept and recaptures the image.
5. After capturing the series of non-annotated lesion(s), the Investigator will annotate the circumference and axes delimiters of lesion with supplied skin pen. Following the same procedure as the non-annotated image capture the site will capture the series of annotated lesion(s) images.

6. Following the session, the Photographer submits the images to Canfield. Upon exiting, the software automatically reads, checksums, encrypts, packages, and duplicates the data to submit to Canfield via internet or removable media submission.
 - a. Internet: A secure, validated, compliant web server set up at Canfield is used for secure transfer of study images by study sites. Images are to be transferred the day they are recorded. Only approved individuals by the Sponsor have access to the website.

The application logs a record of this action to a local database and prompts the Photographer when completed.

7. Upon completion of photography session, the Investigator will log in to the Canfield tracing application may (optional) annotate the lesion and the software will provide measurements (surface area, longest diameter, perpendicular diameter) of the lesion.
8. Trained Canfield staff review the data files for technical quality and acceptability and communicate any comments to the site.

PD-1	Programmed death-1 (receptor)
PR	Partial response
Q3W	Every 3 weeks
R0	Microscopically margin-negative resection; no gross or microscopic tumor remaining in the primary tumor bed
R1	Removal of all macroscopic disease; microscopic margins are positive for tumor
RECIST	Response Evaluation Criteria in Solid Tumors
Regeneron	Regeneron Pharmaceuticals, Inc.
SAE	Serious adverse event
SAF	Safety analysis set
SAP	Statistical analysis plan
SAS	Statistical Analysis System
SD	Stable disease
SOC	System organ class
TEAE	Treatment-emergent adverse event

1. OVERVIEW

The purpose of the statistical analysis plan (SAP) is to ensure the credibility of the study results by pre-specifying the statistical approaches for the analysis of study data prior to database lock. The SAP is intended to be a comprehensive and detailed description of the strategy and statistical methods to be used in the analysis of data for R2810-ONC-1901 study.

This plan may be revised during the study to accommodate protocol amendments and/or to make changes to adapt to unexpected issues in study execution and/or data that affect planned analyses. The final plan, if revised, will document all changes and be issued prior to database lock.

1.1. Background/Rationale

Cutaneous squamous cell carcinoma (CSCC) is a malignant proliferation of epidermal keratinocytes with invasion of the dermis and is distinguished from non-invasive precursor lesions such as actinic keratoses (Nehal, 2018). The precise incidence of CSCC is not known because it is not included in most cancer registries; however, CSCC is thought to be the second most common non-melanoma skin cancer, with an increasing incidence in recent decades (Lomas, 2012)(Que, 2018)(Rogers, 2010).

LIBTAYO® (cemiplimab) is approved in the United States, Canada, and Brazil for the treatment of patients with metastatic cutaneous squamous cell carcinoma or patients with locally advanced cutaneous squamous cell carcinoma who are not candidates for curative surgery or curative radiation. In the United States, it is approved with a suffix as cemiplimab-rwlc.

In an ongoing, investigator-initiated phase 2 pilot study at MD Anderson Cancer Center (NCT03565783), 20 patients with stage III to IV (M0) CSCC received 2 doses of neoadjuvant cemiplimab (350 mg Q3W). Clinical results indicate pCR rates were achieved in a clinically meaningful proportion of patients. All 20 patients were able to undergo surgical resection, and no patient developed unresectable or metastatic disease during the neoadjuvant treatment period.

To extend these encouraging preliminary results, this multicenter study proposes the administration of cemiplimab in the neoadjuvant setting prior to surgery for patients with stage II to stage IV (M0) CSCC in which the primary endpoint is pCR per independent central review. Patients with stage III or IV (M0) CSCC of head/neck, extremity, or trunk are eligible, as well as selected patients with stage II CSCC (≥ 3 cm longest diameter lesion in an aesthetically-sensitive region).

Adjuvant cemiplimab treatment is an appropriate option in the context of a clinical trial. In view of the high efficacy of cemiplimab against advanced CSCC and the positive phase 3 results among other anti-PD-1 antibodies in the adjuvant setting for melanoma patients, it is appropriate to evaluate cemiplimab in the post-operative setting. Therefore, Part 2 of this study allows adjuvant cemiplimab in patients who have not experienced disease progression or unacceptable toxicity during Part 1 (the neoadjuvant portion) of the study. The data from Part 2 could inform the development of a future randomized trial to define adjuvant therapy for patients with CSCC. However, the primary objective of this study is to assess neoadjuvant cemiplimab, not adjuvant therapy.

1.2. Study Objectives

1.2.1. Primary Objectives

The primary objective of the study is to evaluate the efficacy of neoadjuvant cemiplimab as measured by pCR rate per independent central pathology review.

1.2.2. Secondary Objectives

The secondary objectives of the study are:

- To evaluate the efficacy of neoadjuvant cemiplimab on measures of disease response, including:
 - Major pathologic response (mPR) rate per independent central pathology review
 - pCR rate and mPR rate per local pathology review
 - ORR prior to surgery, according to local assessment using RECIST 1.1
- To evaluate the efficacy of neoadjuvant cemiplimab on event free survival (EFS), disease free survival (DFS), and overall survival (OS)
- To evaluate the safety profile of neoadjuvant cemiplimab
- To assess change in surgical plan (ablative and reconstructive procedures) from the screening period to definitive surgery, both according to investigator review and independent surgical expert review
- To assess change in post-surgical management plan (radiation, chemoradiation, or observation) from the screening period to post-surgery pathology review, both according to investigator review and independent surgical expert review

1.2.3. Exploratory Objectives

The exploratory objectives of the study are:

- To explore baseline tumor markers for associations with treatment responses, peripheral and tumor measures associated with cemiplimab mechanism of action, and discovery of other potential predictive markers of efficacy or safety
- To describe patterns of failure (locoregional versus distant) in patients who experience disease recurrence following surgery
- To evaluate the cost implication due to changes in surgical plan during screening period versus actual surgical procedure performed
- To evaluate the cost implication due to changes in post-surgical management plan during screening period versus actual post-surgical management
- To assess the immunogenicity of cemiplimab
- To assess health-related quality of life in patients with CSCC who receive neoadjuvant cemiplimab

1.2.4. Modifications from the Statistical Section in the Final Protocol

- The full analysis set (FAS) includes enrolled patients who received at least one dose of cemiplimab.
- Subgroup efficacy analysis was removed.

1.2.5. Revision History for SAP Amendments

This is the first version of the SAP, based on the original study protocol of R2810-ONC-1901 dated July 16, 2019.

2. INVESTIGATION PLAN

2.1. Study Design

This is a single-arm, open label, multicenter phase 2 study for patients with stage II to IV (M0) CSCC who are candidates for surgery, but who have an increased risk of recurrence and/or risk of disfigurement or loss of function.

The study consists of 2 parts:

- Part 1 (neoadjuvant): A screening period of up to 28 days, a treatment period of up to 12 weeks, and surgery after up to 12 weeks of treatment. Part 1 of the study supports the primary endpoint.
- Part 2 (adjuvant): Optional post-surgery cemiplimab treatment for up to 48 weeks (or radiation therapy, or observation only, at investigator discretion)

After Part 2 of the study, patients will be followed for a period of up to 3 years.

2.2. Sample Size and Power Considerations

Seventy-two (72) patients will be required to provide 90% power to reject a null hypothesis of a pCR rate of 25% at a 2-sided significance level of 0.05 if the true pCR rate is 44%.

The sample size will be further increased by 5% to account for patients who prematurely withdraw from the study. Hence, the total sample size will be approximately 76 patients. Patients who discontinue treatment early and/or withdraw from the study will not be replaced. The 95% binomial exact confidence intervals for observed pCR with 76 patients is provided in [Table 1](#).

The non-clinically meaningful pCR rate of 25% will be excluded using the lower limit of 95% exact CI if the observed pCR rate is 36.8% or more.

Table 1: The 95% Binomial Exact Confidence Intervals for Observed pCR with a Sample Size of 76 Patients

Number of pCR patients	Observed pCR rate	95% CI – lower	95% CI – upper
23	0.303	0.202	0.419
24	0.316	0.214	0.433
25	0.329	0.225	0.446
26	0.342	0.237	0.460
27	0.355	0.249	0.473
28	0.368	0.261	0.487
29	0.382	0.272	0.500
30	0.395	0.284	0.514
31	0.408	0.296	0.527

Number of pCR patients	Observed pCR rate	95%CI – lower	95% CI – upper
32	0.421	0.309	0.540
33	0.434	0.321	0.553

2.3. Study Plan

Treatment in Part 1 (Neoadjuvant): After a screening period of up to 28 days, patients will receive cemiplimab 350 mg IV Q3W for up to 4 doses over 12 weeks (day 1, 22±3, 43±3, and 64±3) or until disease progression, unacceptable toxicity, or withdrawal of consent. Patients will undergo 2 tumor response assessments (via imaging) during Part 1. The first imaging assessment occurs prior to the third dose of cemiplimab on day 43 and the second imaging assessment occurs prior to surgery. If a patient meets criteria to discontinue cemiplimab during the 12-week neoadjuvant period, the treating physician may divert the patient to surgery at an earlier time.

Treatment in Part 2 (Adjuvant): Part 2 of the study will begin following surgery. Patients will have the option to receive cemiplimab treatment (350 mg IV Q3W) for up to 48 weeks (16 doses) or until unacceptable toxicity, disease recurrence, or withdrawal of consent. The first dose of adjuvant cemiplimab will occur at 3 weeks (±3 days) after end of treatment in Part 1 (EOT1). During this part of the study, patients will undergo additional evaluation approximately every 15 weeks. At the discretion of the investigator, patients may alternatively receive adjuvant radiation therapy or enter an observation-only period.

Patients who do not experience disease progression (pre-surgery) or disease recurrence (post-surgery) will be followed for an additional nontreatment period of up to 3 years with clinical assessments performed approximately every 4 months (first 2 years) or every 6 months (the third year).

3. ANALYSIS POPULATIONS

In accordance with guidance from the International Conference of Harmonization of Technical Requirements for Registration of Pharmaceuticals for Human Use (ICH) guideline ICH E9 Statistical Principles for Clinical Trials (ICH, 1998), the following population of analysis will be used for all statistical analysis.

3.1. The Full Analysis Set (FAS)

The full analysis set (FAS) will include all enrolled patients who have received at least one dose of cemiplimab. Efficacy endpoints will be analyzed using the FAS.

3.2. The Safety Analysis Set (SAF)

The safety analysis set (SAF) will include all enrolled patients who have received at least one dose of cemiplimab. Treatment compliance/administration and all clinical safety variables will be analyzed using the SAF.

3.3. Immunogenicity Analysis Sets

The ADA analysis set includes all patients who received study drug and had at least 1 non-missing ADA result following the first study dose. Patients will be analyzed according to the treatment actually received.

3.4. Exploratory Pharmacodynamic and Biomarker Analysis Set

The biomarker analysis set for each analysis includes all patients who received cemiplimab and who have data available from baseline.

4. ANALYSIS VARIABLES

4.1. Demographic and Baseline Characteristics

The following demographic and baseline characteristics variables will be summarized:

- Age at screening in years (quantitative and qualitative variable: <65, ≥65 years)
- Sex (Male, Female)
- Race (American Indian/Alaskan Native, Asian, Black/African American, Native Hawaiian/Other Pacific Islander, White, and Other)
- Ethnicity (Hispanic/Latino or not)
- Weight (kg)
- Height (cm)
- Body mass index (BMI) calculated from weight and height: $\text{weight (kg)} / [\text{height (m)}]^2$
- ECOG performance status (0, 1)

Baseline tumor characteristics variables include:

- Tumor type
- Time from initial diagnosis to first study dose
- Cancer stages at initial diagnosis

4.2. Medical History

Medical history will be coded using Medical Dictionary for Regulatory Activities (MedDRA®).

4.3. Pre-Treatment / Concomitant Medication

Medications/Procedures will be recorded from the day of informed consent until the end-of-study (EOS) visit. Medications will be coded using WHO Drug Dictionary (WHODD).

Prior cancer related medications/procedures: medications taken, or procedures performed prior to administration of the study drug.

Pre-treatment medications/procedures: non-study medications for which administration started and discontinued before a patient received the first dose of study drug.

Concomitant medications/procedures: any treatment administered from the time of informed consent until 90 days after the last study treatment or start of another systemic anticancer therapy, whichever comes first, will be considered concomitant treatment. This includes medications that were started before the study and are ongoing during the study, as well as any therapies started in the follow-up period to treat treatment related AEs.

Post treatment anti-cancer medications/procedures: anti-cancer medications and other anti-cancer therapies that started after discontinuation of the study drug.

4.4. Efficacy Variable

4.4.1. Primary Efficacy Variable

The primary objective of the study is to evaluate the efficacy of neoadjuvant cemiplimab as measured by pathologic complete response (pCR) rate per independent central pathology review. Pathologic complete response (pCR) is defined as absence of viable cancer cells in the surgical pathology sample.

4.4.2. Secondary Efficacy Variables

The secondary efficacy variables include:

- Major pathologic response (mPR) rate per independent central pathology review: mPR is defined as failure to achieve pCR but $\leq 10\%$ viable cancer cells in the surgical pathology sample.
- pCR rate and mPR rate assessed by local pathology review: pCR and mPR will be assessed by local pathology review.
- Objective response rate (ORR) prior to surgery by investigator assessment: ORR is determined by the proportion of patients with CR or PR based on investigator-assessed evaluation using RECIST 1.1 (Eisenhauer, 2009), where there is no requirement for confirmation of CR or PR. The objective response will be measured from the first dose of neoadjuvant cemiplimab to surgery or any other new anti-cancer therapy.
- Event free survival (EFS) is defined as time from first dose of neoadjuvant cemiplimab to the first of any of the following events: progression of disease that precludes surgery, inability to undergo complete resection (R0 or R1), disease recurrence (local, regional, or distant) for patients who undergo complete resection (R0 or R1), or death due to any cause.
 - Patients who do not have an EFS event without initiation of a new anti-cancer therapy will be censored at the last evaluable tumor assessment.
 - Patients who do not have an EFS event but initiate a new anti-cancer therapy, will be censored at the last evaluable tumor assessment prior to or on the date of new anti-cancer therapy.
 - Patients who do not have any evaluable post-baseline tumor assessment and do not die will be censored on the date of first study treatment.
- Disease free survival (DFS) is defined for patients who are free of disease (R0 or R1 resection) at completion of surgery as time from date of surgery until first recurrence (local, regional, or distant) or death due to any cause.
 - Patients who do not have recurrence of tumor and alive without initiation of a new anti-cancer therapy will be censored at the last evaluable tumor assessment.

- Patients who do not have recurrence of tumor and alive, but initiate a new anti-cancer therapy, will be censored at the last evaluable tumor assessment prior to or on the date of new anti-cancer therapy.
- Patients who do not have any tumor assessment after surgery and do not die will be censored on the date of surgery.
- Overall survival (OS) is measured from the start of treatment until death due to any cause. Patients who do not die will be censored at the last date that patient is documented to be alive.

For all the above time-to-event variables, the time to event (day) is the date of event/censor - the date of first study treatment + 1.

- Change in surgical plan in the screening period versus actual surgery after neoadjuvant cemiplimab both according to investigator review and independent surgical expert review is measured by descriptive analysis. For investigator review, the overall treatment plan formulated at a multidisciplinary tumor board, description of planned/actual surgery resection, description of planned/actual reconstruction (if applicable) and planned/actual length of inpatient hospital stay after surgery will be collected.
- Change in post-surgical management plan in the screening period versus actual post-surgical management both according to investigator review and independent surgical expert review is measured by descriptive analysis. For investigator review, radiotherapy method, radiation fractionation, duration of therapy, total dose, and adjuvant chemoradiation type (if applicable) will be collected.

For independent review, variables to assess changes in planned surgery and post-surgical management will be described in a separate charter.

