4. ENDPOINTS

For endpoints measuring pCR, mPR, and ORR (Part 1 of the study), patients will be assessed at the time of surgery (12 weeks). Event free survival (EFS) and OS will be assessed from the first dose of neoadjuvant cemiplimab until completion of follow-up. Disease free survival (DFS) will be assessed from surgery until completion of follow-up. Event free survival (EFS), DFS, and OS assessment will continue until all enrolled patients have completed follow-up, a total duration of approximately 4 years and 3 months.

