7. Imaging assessments performed in Part 2 of the study should be the same as those performed in Part 1 of the study, for a given patient. Imaging requirements include CT/MRI and optional digital photography (see Section 9.2.2.3).
8. Tumor biopsy should be attempted in all cases of suspected recurrence or suspected SPT (Section 9.2.2.4), unless there is an unacceptable safety risk associated with biopsy in a particular patient. Biopsy information regarding recurrences or SPTs (or safety reason explaining why biopsy was not performed) will be documented in eCRF. See Section 9.2.2.7 for additional information on biopsies.
9. Blood samples for ADA assessment in serum will be collected at week 0 of Part 2 (before infusion), at week 15 of Part 2 (before infusion), and at any time at EOT2 or the early termination visit. In Part 2, ADA assessment will only be performed for patients receiving adjuvant cemiplimab. Pharmacokinetic (PK) analyses may be performed on ADA samples if appropriate as part of safety assessment at the individual patient level.
10. The EORTC QLQ-C30 should be administered to during the week 15 visit only.

Table 4: Schedule of Events for Follow-Up After Part 2 of the Study

Study Procedure ¹	Years 1 and 2	Year 3
Frequency	Every 4 months (± 30 days)	Every 6 months (± 45 days) ²
Complete Physical Examination and ECOG PS	X	X
Vital Signs and Weight	X	X
Hematology	X	X
Blood Chemistry	X	X
TSH (with reflex T3, free T4)	X	X
CT/MRI ³	X	X
Plasma ctDNA Sample	X	X
ADA Sample	X ⁴	
Tumor Biopsy	At any time that recurrence or SPT is suspected ⁵	
Concomitant Medications	← continuous monitoring →	
Adverse Events	← continuous monitoring →	

ADA=anti-drug antibody; ctDNA=circulating tumor deoxyribonucleic acid; ECOG PS=Eastern Cooperative Oncology Group Performance Status; SPT=second primary tumor; TSH=thyroid-stimulating hormone

9.1.3. Footnotes for Table 4: Schedule of Events for Follow-Up After Part 2 of the Study

- The first follow-up visit will occur 4 months after the EOT2 visit. Patients who receive radiation therapy or observation only in Part 2 are only required to follow the imaging assessments (and biopsy, if indicated) in [Table 4](#).
- The last visit of year 3 will constitute the end of follow-up. However, patients will continue to be followed for survival until death or until study closure.

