9.1.7. Survival Follow-Up

Survival follow-up begins after completion of the follow-up schedule of events in Table 4 (including patients who follow an imaging schedule), or after disease recurrence. Any patient who fails to achieve complete surgical resection (defined as R0 or R1) will also enter survival follow-up. Patients in survival follow-up will be contacted quarterly (telephone is acceptable) for survival status and treatment status (subsequent anticancer systemic therapy) until the EOS.

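### EFS and DFS count deaths after imaging has ended but censor survivors at their last scan, so one late death can create a false Kaplan-Meier tail and a false median

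*SAP*

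**What the plan says.** **Events.** SAP 4.4.2 ends the list of EFS events with "disease recurrence (local, regional, or distant) for patients who undergo complete resection (R0 or R1), or death due to any cause". DFS is "time from date of surgery until first recurrence (local, regional, or distant) or death due to any cause". Neither definition limits how long after the last scan a death may fall and still count.

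**Censoring.** For EFS: "Patients who do not have an EFS event without initiation of a new anti-cancer therapy will be censored at the last evaluable tumor assessment". The DFS rule applies only to the living: "Patients who do not have recurrence of tumor and alive without initiation of a new anti-cancer therapy will be censored", again at the last evaluable scan.

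**Follow-up.** Table 4 of the protocol schedules CT/MRI through year 3 of follow-up, and its footnote 2 (section 9.1.3) makes the final year-3 visit the end of follow-up. The same footnote continues: "However, patients will continue to be followed for survival until death or until study closure". Section 9.1.7 agrees: "Survival follow-up begins after completion of the follow-up schedule of events in Table 4". That stage consists of quarterly contacts about survival and treatment status, with no scans scheduled. Section 6.1.6 ends the study at the last patient's last visit.

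**Intended window.** Protocol section 4 says: "Event free survival (EFS) and OS will be assessed from the first dose of neoadjuvant cemiplimab until completion of follow-up". It treats DFS the same way from surgery, and gives a total of about 4 years 3 months. The SAP does not repeat this limit.

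**Outputs.** SAP 5.6.2 reports medians with 95% CIs, Kaplan-Meier curves and estimates at time points that it does not name. SAP section 5 plans an updated analysis once post-treatment follow-up or the study has ended.

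**The concern.** Take two patients who finish Table 4 without an event. One is alive at study closure and leaves the risk set at the last scan. The other dies during the survival contacts and stays in the risk set until death. How long a patient remains at risk therefore depends on whether that patient later dies. Beyond the last scans, the risk set contains only patients who will die.

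A Kaplan-Meier step has size 1/(number at risk). With one or two patients at risk, one death can pull a high plateau to zero or near it, although many patients are known to be alive. A median that has not been reached would then be reported as reached, at a time set by one death. This has nothing to do with the separate rule on new anti-cancer therapy; it affects patients who never had any.

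**Working it through.** **1. Where imaging ends.** Protocol inputs: surgery at nominal day 85; EOT1 30 days later; week 0 of Part 2 a further 21 days later; Part 2 to week 48; then 3 years of follow-up.

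85 + 30 + 21 + 48×7 + 3×365.25 = 1,567.75 days = 4.29 years, or 4 years 3.5 months. This reproduces the protocol's total of about 4 years 3 months, with no accrual time included. Taking visit windows at their extremes gives 1,496.75 to 1,659.75 days (4.10 to 4.54 years).

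**2. How long death-only follow-up lasts.** It runs from a patient's own last scan to the last patient's last visit. For the first patients enrolled, that is roughly the length of accrual, which the documents do not state.

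**3. One late death, with the SAP rule applied as written.** Illustration: 76 patients; k events by day 1,000; all other last scans spread evenly over days 1,508 to 1,628 (nominal ±60 days); one patient dies after imaging ends. Before that death S = (76 − k)/76, because nobody has yet been censored when the earlier events occur. At the death, S is multiplied by 1 − 1/(number at risk).

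| Earlier events k | S before | Death at day 1,613 (at risk) | Death at day 1,768 (1 at risk) |
|---|---|---|---|
| 8 | 68/76 = 0.895 | 0.795 (9) | 0 |
| 16 | 60/76 = 0.789 | 0.702 (9) | 0 |
| 24 | 52/76 = 0.684 | 0.599 (8) | 0 |
| 32 | 44/76 = 0.579 | 0.496 (7) | 0 |

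For k = 16: 0.789 × (1 − 1/9) = 0.702, and 0.789 × (1 − 1/1) = 0. In every row of the last column the median becomes day 1,768 (4.84 years); without that death it is not reached. With 32 earlier events, even the smaller step crosses 0.5 and yields a median.

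**4. How often.** Simulation of 76 patients, 1,000 runs per setting. Assumptions, none of them in the documents: uniform accrual over 6 to 24 months; 60%, 75% or 85% event-free at the end of imaging; 1%, 3% or 5% deaths per year afterwards; last scans at 1,568 ± 60 days. With 75% event-free and 3% deaths per year:

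| Accrual (months) | Curve ends at zero | Median reported |
|---|---|---|
| 6 | 29% | 30% |
| 12 | 51% | 51% |
| 18 | 66% | 66% |
| 24 | 77% | 77% |

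Over the whole grid, the curve ends at zero in 10% to 94% of runs. If deaths after the end of imaging do not count, it never does. A median is then reported in 0.2% of runs with 75% event-free, 0% with 85%, and 9% with 60%, where the medians are genuine.

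**5. What does not change.** Curves with and without the late deaths coincide until the earliest last scan, 4.10 years from first dose. For DFS timed from surgery, the earliest is 1,496.75 − 75 = 1,421.75 days, or 3.89 years.

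**The case against.** The best answer is that the protocol already closes the window. Section 4 runs EFS and DFS to completion of follow-up, and footnote 2 to Table 4 says when that is. The 4 years 3 months matches one patient's calendar, which suggests a per-patient window. SAP 1.2.4 lists two departures from the protocol's statistical section, and a change of window is not among them. This shows what was probably intended. It does not settle the matter: section 4 words OS the same way, although OS plainly continues in survival follow-up, and adds that assessment goes on until all enrolled patients have finished. A programmer working from SAP 4.4.2 would count the late death.

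Second, EFS and DFS are descriptive secondary endpoints with no test attached, and only event-free patients who complete Table 4 and then die cause the problem. Patients followed for survival after recurrence or incomplete resection already have an EFS event. A fall to exactly zero also needs a death later than every other patient's last scan. All of this stands, and it limits the severity.

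Third, recoding deaths as censored can itself be outcome-dependent. That would be so if only the deaths were moved. It is not so if the window closes at the same scheduled visit for everyone, whatever their later vital status.

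A reader might also infer that the fixed-time estimates in SAP 5.6.2 are unreliable. The documents do not support that for time points up to about 4 years, where the curves are the same.

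**Conclusion.** The SAP rule as written gives a wrong EFS and DFS tail in the updated analysis whenever an event-free patient dies after the end of scheduled imaging. The single-death result needs no accrual or mortality assumption: with 1 at risk the curve goes to zero and a false median appears; within the cluster of last scans the false step is smaller, such as 0.789 to 0.702.

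The frequency cannot be pinned down. The range of 10% to 94% rests on assumed accrual, death rate and event-free share. It shows that the problem is far from remote, but does not predict its size in this trial. It would be tempting to treat this as critical. The documents do not support that: pCR and OS are untouched, estimates to about 4 years are unchanged, and no hypothesis test depends on EFS or DFS. It should be fixed before the updated analysis.

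**What to change.** Carry the protocol's window (section 4, with footnote 2 to Table 4) into SAP 4.4.2, for example:

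*EFS and DFS are assessed through the patient's last scheduled Table 4 visit (end of year 3 of follow-up). Every patient who completes that visit without an event is censored at the last evaluable tumor assessment, regardless of later vital status. Deaths after that visit count in OS only.*

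Print numbers at risk under the EFS and DFS curves. Add a sensitivity analysis that counts all deaths and censors event-free survivors at the date last known alive, so that survivors and patients who die are followed over the same period. No scans are scheduled in that period, so recurrences may be missed; it should support the main analysis, not replace it.

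The cost is a short SAP amendment and one extra run. The downside is that a few late deaths leave EFS and DFS; they remain in OS. Fixing the rule before the data are seen avoids a later choice between two very different tails.
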